11.5.3. Safety

ECG Parameters
ECG parameters will be collected in triplicate at each time point. The mean of the triplicate measurements will be calculated for each ECG parameter and used as the value for that time-point. For ECG findings and PCI criteria, all three ECGs will be considered and the worst case result will be summarised. For PCI criteria comparing to baseline, the mean of the triplicate measurements at baseline will be used as the baseline value.
ECG Findings
For the summary of ECG findings (where assessed in triplicate at each time-point) a 'worst case' assessment for each subject will be derived, so that the number of subjects and percentages sum to 100% within each time-point.
RR Interval

 RR is not collected for machine read ECG. IF RR interval (msec) is not provided directly, then RR can be derived as: 
 [1] If QTcB is machine read & QTcF is not provided, then: $RR = \left[\left(\frac{QT}{QTcB} \right)^2 \right] * 1000$ [2] If QTcF is machine read and QTcB is not provided, then: $RR = \left[\left(\frac{QT}{QTcF} \right)^3 \right] * 1000$

ECG Parameters

- If ECGs are manually read, the RR value preceding the measurement QT interval should be a collected value THEN do not derive the RR interval if it is available (i.e., collected on the eCRF). If the RR interval is not available then it may be derived using the formula above.

Corrected QT Intervals

- Where QTcB and/or QTcF are reported in the eCRF then these reported values should be used (with no re-derivation).
- When not entered directly in the eCRF, corrected QT intervals by Bazett's (QTcB) and Fredericia's (QTcF) formulas will be calculated, in msec, depending on the availability of other measurements. IF RR interval (msec) is provided or derived then missing QTcB and/or QTcF will be derived as:

$$QTcB = \frac{QT}{\sqrt{\frac{RR}{1000}}}$$

$$QTcF = \frac{QT}{3\sqrt{\frac{RR}{1000}}}$$

- If only QTc (other method of correction) is reported then QTcB and QTcF are unable to be derived. Then data for QTc (other method of correction) will be summarised. This will be presented as a separate parameter.

QTcF / QTcB Categories

- QTcB and QTcF values will be summarised using the following categories:
- Absolute: <450 msec; ≥450 to 480 msec; ≥480 to <500 msec; and ≥500 msec
- Change from baseline: 0 to <30 msec; ≥30 to <60 msec, and ≥60 msec.
- The mean of the triplicate measurements at each visit will be used in these summaries.
- Data for QTc (other method of correction) will also be presented as a separate parameter in these summary tables.

Adverse Events

AE Density

- AE density, also referred to as event density, will be calculated as the number of events in a given period divided by the total person time on treatment (in years) of subjects at risk at the beginning of the same period. All AE densities will be presented per 100 person-years (by multiplying the above defined statistics by 100). i.e.:
- On-therapy AE density = 100 x number of on-therapy AEs/total person time on treatment (years)
- Note: see exposure derivations for total person time on treatment calculation.

AE's of Special Interest

 Cardiovascular Events – investigator reported: defined as events reported by the investigator on the specific AESI eCRFs (congestive heart failure CRF; cerebrovascular events/stroke and transient ischemic attack CRF; deep vein thrombosis/pulmonary embolism CRF; myocardial infarction / unstable angina CRF; peripheral arterial thromboembolism CRF; pulmonary hypertension CRF; revascularisation CRF; valvulopathy CRF; and arrhythmias CRF) Atrial Fibrillation / Atrial Flutter – investigator reported: defined as events reported by the investigator on the specific atrial fibrillation/atrial flutter eCRF. Pneumonia – investigator reported: defined as events reported by the investigator on the specific pneumonia eCRF. Pancreatitis – investigator reported: defined as events reported on the pancreatitis eCRF. Pancreatitis – positively adjudicated by pancreatic adjudication committee (PAC): defined as events reported on the pancreatitis eCRF and adjudicated as pancreatitis by the PAC. Adjudicated as pancreatitis is defined as the probability of pancreatitis reported as definite or possible by the PAC. Thyroid Adverse Events – investigator reported: Thyroid adverse events are events reported by the investigator on the specific AESI eCRF (Thyroid cancer, nodule and goiter diagnosis). Gastrointestinal Events: defined as AEs coded to the MedDRA SOC of gastrointestinal disorders Injection Site Reaction – investigator reported: defined as events reported by the investigator on the specific investigational product injection site reactions eCRF Systemic Allergic Reaction – investigator reported: Potential systemic allergic reactions are events reported by the investigator on the specific AESI eCRF (hypersensitivity – syndrome/symptoms). Liver Monitoring/Stopping Events – investigator reported: defined as events reported by the investigator on the specific liver event pages in the eCRF. Liver events as defined in the protocol. Liver Events: defined as events identified by a customised MedDRA query. Renal Impairment – investigator reported: defined as events reported by the investigator on the specific renal impairment eCRF. Diabetic ketoacidosis (DKA): defined as events identified by a customised MedDRA query. Appendicitis: defined as events identified by a customised MedDRA query. Pancreatic Cancer: defined as events identified by a customised MedDRA query. Malignant Neoplasms: defined as events identified by a standard MedDRA query.
GI Events Over Time

 For the summary of GI events over time (by week), each week will include those subjects with onset of the event during that particular week and also those subjects with the event that started during a previous week but has not resolved.

Subject-Reported Hypoglycaemic Events	
Reporting	
 Subjects reported hypoglycaemic events in an e-diary, which will be integrated with the clinical database at the end of the study. The investigator reviewed the hypoglycaemic events and any that met the definition of an SAE were also reported as such in the SAE CRF. Adverse event summaries therefore do not include hypoglycaemic events, unless reported in the SAE dataset by the investigator. Subject-reported hypoglycaemia summaries include all reported events (on-therapy and post-therapy events).
Data selection/derivation	

 Subject-reported hypoglycaemic events reported in the e-diary will be integrated into the clinical database using 3 datasets: 
 DRE (start date/time of event, end date/time of event) FADRE (questions about treatment, assistance and symptoms) LAB (plasma glucose reading at time of event) To select the e-diary subject-reported hypoglycaemic event glucose results from the laboratory dataset, select only records with visit ="HYPOGLYCAEMIC EVENT" In order to combine information from the different datasets for a subject's hypoglycaemia event, a combination of subject id and DREREFID must be used. The DREREFID variable links the components of a single hypoglycaemia event across DRE, FADRE and LAB datasets 	
ADA Category	

 Subjects reported hypoglycaemic events will be classified as defined by the ADA Workgroup on Hypoglycaemia [Sequist, 2013]. Severe Hypoglycaemia: an event requiring assistance of another person to actively administer carbohydrates, glucagon, or take other corrective actions. Plasma glucose concentrations may not be available during an event, but neurological recovery following the return of plasma glucose to normal is considered sufficient evidence that the event was induced by a low plasma glucose concentration Documented Symptomatic Hypoglycaemia: an event during which typical symptoms of hypoglycaemia are accompanied by a measured plasma glucose concentration ≤ 70 mg/dL (≤ 3.9 mmol/L) Asymptomatic Hypoglycaemia: an event not accompanied by typical symptoms of hypoglycaemia but with a measured plasma glucose concentration ≤ 70 mg/dL (≤ 3.9 mmol/L) Probable Symptomatic Hypoglycaemia: an event during which symptoms typical of hypoglycaemia are not accompanied by a plasma glucose determination but that was presumably caused by a plasma glucose concentration ≤ 70 mg/dL (≤ 3.9 mmol/L) Pseudo Hypoglycaemia: an event during which the person with diabetes reports any of the typical symptoms of hypoglycaemia with a measured plasma glucose concentration > 70 mg/dL (> 3.9 mmol/L) but approaching that level Events will be classified into ADA categories based on the following questions: 
 1. 'Did you require someone else's help to get the treatment needed?' (Yes/No) 2. 'Any symptoms?' (Yes/No) 	

Subject-Reported Hypoglycaemic Events

- 3. 'Lowest plasma glucose reading at the time of the event' (numeric value/Not Done)
- Note: Glucose readings from subject-reported hypoglycaemic events initial reported in the eDiary are identified in the laboratory dataset by VISIT='HYPOGLYCAEMIC EVENT'.
- Glucose will be presented in mmol/L. A glucose value reported in mg/dL will be converted to mmol/L by multiplying the value by 0.05551.

The ADA categories will be assigned based upon the questions above as follows:

- Severe: Required assistance (Q1) = Yes
- Documented Symptomatic: Symptoms (Q2) = Yes and Glucose reading (Q3) = ≤ 3.9 mmol/L
- Asymptomatic: Symptoms (Q2) = No or missing and Glucose reading (Q3) = ≤ 3.9 mmol/L
- Probable Symptomatic: Symptoms (Q2) = Yes and Glucose reading (Q3) = Not done
- Pseudo: Symptoms (Q2) = Yes and Glucose reading (Q3) = > 3.9 mmol/L
- i.e.,

ADA classification	Required Assistance	Symptoms	Glucose Reading (mmol/L)
Severe	Yes	Any*	Any*
Documented Symptomatic	No or missing	Yes	$0 < \text{glucose} \leq 3.9$
Asymptomatic	No or missing	No or missing	$0 < \text{glucose} \leq 3.9$
Probable Symptomatic	No or missing	Yes	Glucose = 0 or missing
Pseudo	No or missing	Yes	Glucose > 3.9

* includes missing values

- A subject reported event that does not meet any of the above criteria will not be counted as a hypoglycaemic event (any events will be flagged to the study team for review).
- Only hypoglycaemic events that subjects record in the glucose meter will be included in the summaries of subject-reported hypoglycaemic events. Glucose readings reported, for example, as part of standard laboratory testing or the 7-point glucose profile will not be included.
- Each event will be assigned to one ADA category, but a subject may report events from multiple ADA categories. A subject will appear in all ADA categories they experience.

Daytime/Nocturnal Events

- Subjects report the start date/time of a hypoglycaemia event. The start time of event will be used to classify the event as daytime or nocturnal.
- Daytime Hypoglycaemia: an event with an onset time between 06:00h and 00:00h (inclusive). i.e., in SAS time format (secs): start time = 0 or start time > 21541
- Nocturnal Hypoglycaemia: an event with an onset time between 00:01h and 05:59h (inclusive). i.e., in SAS time format (secs): $0 < \text{start time} \leq 21540$
- Events with a missing start time will be classified as Daytime events

Time periods (3 monthly intervals)

 Events will be assigned to time periods will are defined using the following categories: Baseline to \leqWeek 12: Study day 1 to \leq84 $>$Week 12 to \leqWeek 24: Study day 85 to \leq168 $>$Week 24 to \leqWeek 36: Study day 169 to \leq252 $>$Week 36 to \leqWeek 52: Study day 253 to \leq364 $>$Week 52 to \leqWeek 64: Study day 365 to \leq448
Time periods (2 weekly intervals)

 A summary of events by 2 weekly time periods will also be produced. E.g., Day 1 to Day 14; Day 15 to Day 28; etc.
Denominators for time period summaries

 Summaries of subject-reported events over time will calculate percentages based on the number of subjects at risk of an event within each time period. i.e., the Ns will be expected to decrease over time as subjects withdraw from the study The date of study withdrawal will be used as the end-date of the 'at-risk' period for each subject, as subject-reported hypoglycaemic events are reported throughout the study period i.e., until week 64 or study withdrawal. A subject will not be included as 'at-risk' in a particular period if their study withdrawal date is before the start date of the interval.
Hypoglycaemic Events with Glucose $<3.1\text{mmol/L}$

 Hypoglycaemic events with a plasma glucose $<3.1\text{ mmol/L}$ ($<56\text{ mg/dL}$) will also be identified.
Laboratory Parameters
Only data from the central laboratory will be included in the tables, figures and listings. Data from local laboratories will not be included.
eGFR

 $\text{eGFR} (\text{mL/min}/1.73\text{ m}^2) = 175 \times (\text{S}_{\text{cr}})^{-1.154} \times (\text{Age})^{-0.203} \times (0.742 \text{ if female}) \times (1.212 \text{ if African American})$ eGFR will be calculated based on measured creatinine and associated age. For this purpose, associated age (in whole years) will be calculated with respect to the date of creatinine sample using the imputed date of birth (see Section 11.6.2.1). This derived eGFR will be used for summary tables.
Glucose data not included in laboratory TFLs

 Glucose readings from the MMTT will not be included in any laboratory TFLs. These are identified in SDTM.LB as LBTEST='Glucose' and LBTPTNUM = 10, 20, 30, 40, 50, 60, 70. Finger-stick glucose readings for the MMTT will not be included in any laboratory TFLs. These can be identified in the SDTM.LB dataset using LBTEST='Glucose' and VISIT ne " and LBNAM='NOT APPLICABLE - NO RANGES EXPECTED', LBTPPT=' ' and LBSPEC='BLOOD'. Glucose data from the eDiary card and 72h CGM will not be included in any laboratory TFLs. The glucose data from the eDiary and 72h CGM can be identified in the laboratory domain/dataset (SDTM.LB) as LBTEST = "Glucose" and LBNAM="NOT APPLICABLE – NO RANGES EXPECTED". 
 Subject reported Hypoglycaemic event glucose readings are identified where LBTPT

Laboratory Parameters

(timepoint) = null and visit = null [these can be identified in SI.LAB with visit="HYPOGLYCAEMIC EVENT"]
 
 ○ Routine glucose monitoring readings are identified where LBTPTNUM = 150, 160, 170, 180, 190, 200 corresponding to (OTHER, BEFORE MEAL, AFTER MEAL, AFTER MEDICATION, AFTER SPORT, CONTROL) ○ 7 Point glucose monitoring readings are identified where LBTPTNUM = 80, 90, 100, 110, 120, 130, 140 corresponding to (BEFORE BREAKFAST, 2 HRS AFTER BREAKFAST, BEFORE LUNCH, 2 HRS AFTER LUNCH, BEFORE DINNER, 2 HRS AFTER DINNER, AT BEDTIME). Data directly from the eDiary with VISIT = null. Data recorded into the eCRF with VISIT present (not null). ○ 72h CGM data are identified where LBSPEC='INTERSTITIAL FLUID' and LBMETHOD='TRANSDERMAL MONITORING'.
Laboratory Values Below Limits of Quantification and Repeat Testing

 • Laboratory results that are beyond the limits of quantification will have the inequality sign dropped (<, ≤, >, or ≥) and the quantification limit will be used as the numeric result for summarisation.
Potential Clinical Importance (PCI)

 • The categories for PCI criteria are: Low; Normal; High. • Data will be summarised by nominal visit, but will also include 'any on-therapy visit' and 'any post-baseline visit' categories. These 'any visit' categories will also include unscheduled visits. • The data is summarised using a shift table, comparing the baseline category to the worst case post-baseline category at that time-point (note, worst case is applicable for the 'any visit' categories). The percentages are based on the number of subjects in the treatment group with data for the laboratory test post-baseline at that time-point. Subjects with a missing baseline value are to be assumed to have a normal/within range baseline value. • Worst case can be either High or Low. If a subject has both a decrease 'Low' and an increase 'High', then the subject is counted in both the 'Low' and 'High' categories.
Hepatotoxicity

 • Subjects falling into the following categories will be summarised: 
 ○ ALT ≥3xULN and Total Bilirubin ≥2xULN ○ ALT ≥3xULN and INR >1.5xULN ○ Hepatocellular injury ○ Hepatocellular injury and Total Bilirubin ≥2xULN ○ ALT ≥3xULN, ≥5xULN, ≥8xULN, ≥10xULN, ≥20xULN, ○ Total Bilirubin ≥2xULN ○ ALP ≥2xULN and (Baseline ALP <2xULN or Baseline ALP missing) • Time from first dose of study treatment to first ALT elevation ≥3x (ULN) (days) will be calculated as: $(\text{Date of first ALT } \geq 3\text{xULN}) - (\text{Date of first dose})$ • Further details can be found in the IDSL core standards 'Liver Event Displays'.

Vital Signs
Potential Clinical Importance (PCI)

 The categories for PCI criteria are: Low; Normal; High. Data will be summarised by nominal visit, but will also include 'any on-therapy visit' and 'any post-baseline visit' categories. These 'any visit' categories will also include unscheduled visits. The data is summarised using a shift table, comparing the baseline category to the worst case post-baseline category at that time-point (note, worst-case is applicable for the 'any visit' categories). The percentages are based on the number of subjects in the treatment group with data for the test post-baseline at that time-point. Subjects with missing baseline value are to be assumed to have normal/within range baseline value. Worst case can be either High or Low. If a subject has both a decrease 'Low' and an increase 'High', then the subject is counted in both the 'Low' and 'High' categories.

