6.4.2. Subject-Reported Hypoglycaemia Events

Subjects will be asked to report hypoglycaemic events that occur in a diary, which will be integrated with the clinical database at the end of the study. These hypoglycaemic events that are reported by subjects will be classified as defined by the ADA Workgroup on Hypoglycaemia [[Seaquist, 2013](#)].

Severe Hypoglycaemia

- Severe hypoglycaemia is an event requiring assistance of another person to actively administer carbohydrates, glucagon, or take other corrective actions. Plasma glucose concentrations may not be available during an event, but neurological recovery following the return of plasma glucose to normal is considered sufficient evidence that the event was induced by a low plasma glucose concentration

Documented Symptomatic Hypoglycaemia

- Documented symptomatic hypoglycaemia is an event during which typical symptoms of hypoglycaemia are accompanied by a measured plasma glucose concentration ≤ 70 mg/dL (≤ 3.9 mmol/L)

Asymptomatic Hypoglycemia

- Asymptomatic hypoglycaemia is an event not accompanied by typical symptoms of hypoglycaemia but with a measured plasma glucose concentration ≤ 70 mg/dL (≤ 3.9 mmol/L)

Probable Symptomatic Hypoglycemia

- Probable symptomatic hypoglycaemia is an event during which symptoms typical of hypoglycaemia are not accompanied by a plasma glucose determination but that was presumably caused by a plasma glucose concentration ≤ 70 mg/dL (≤ 3.9 mmol/L)

Pseudo Hypoglycemia

- Pseudo hypoglycaemia is an event during which the person with diabetes reports any of the typical symptoms of hypoglycaemia with a measured plasma glucose concentration > 70 mg/dL (> 3.9 mmol/L) but approaching that level

Any hypoglycemia event, regardless of intensity, that satisfies the definition of an SAE (Section 6.4.10.2) should be categorised as outlined in this section and reported appropriately on the SAE eCRF pages.

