8.2.1.7.1. Cardiovascular Events

Investigators will be required to fill out event specific data collection tools for the following AEs and SAEs:

- Myocardial infarction/unstable angina
- Congestive heart failure
- Arrhythmias including atrial fibrillation/flutter
- Valvulopathy
- Pulmonary hypertension
- Cerebrovascular events/stroke and transient ischemic attack
- Peripheral arterial thromboembolism
- Deep venous thrombosis/pulmonary embolism
- Revascularisation

Cardiovascular events are reported by the Investigator on specific eCRFs for each event. These events are not adjudicated.

8.2.1.7.2. *Atrial Fibrillation/Atrial Flutter*

In addition to being included within the cardiovascular event ‘arrhythmias’ above, atrial fibrillation/atrial flutter events are also reported by the Investigator on a specific atrial fibrillation/atrial flutter eCRF.

8.2.1.7.3. *Subject-Reported Hypoglycaemic Events*

Subject-reported hypoglycaemia summaries include on-therapy and post-therapy events.

Hypoglycaemic events are reported in a subject eDiary; any meeting the SAE criteria are also reported in the adverse event data. The following summaries use subject-reported data (see Section 11.5.3). Incidence will be reported using the number and percentage of subjects experiencing events and the number of events.

Incidence of hypoglycaemia (in total and by each category as defined by ADA criteria) overall and in 3 monthly intervals will be summarised by treatment group.

Incidence of daytime hypoglycaemia (in total and by ADA category) and nocturnal hypoglycaemia (in total and by ADA category) will be summarised by treatment.

Incidence of hypoglycaemia with plasma glucose <3.1 mmol/L (< 56mg/dL), regardless of symptoms, will be summarised by treatment.

The number and percentage of subjects reporting hypoglycaemia during each two week period will be presented by treatment group. A summary table and plot will be produced. In addition, the number of hypoglycaemic events reported per subject during each two week period will be presented by treatment group. A summary table will be produced, and the mean number of hypoglycaemic events reported per subject during each two week period will be plotted.

Further exploratory analysis may be done, depending on the amount of missing data.

A by-subject listing of all subject-reported hypoglycaemic events will be produced.

Note: subject-reported hypoglycaemic events are also summarised as part of the secondary efficacy endpoints.

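### The SAP's rule for pseudo-hypoglycaemia has no upper glucose limit, so unassisted symptomatic events with clearly non-low readings count in the descriptive hypoglycaemia totals

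*SAP*

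**What the plan says.** Protocol 6.4.2 lists five ADA categories for subject-reported events. The fifth reads: "Pseudo hypoglycaemia is an event during which the person with diabetes reports any of the typical symptoms of hypoglycaemia"; the reading that goes with it must be "> 70 mg/dL (> 3.9 mmol/L) but approaching that level". SAP 11.5.3 repeats that definition in its narrative: "with a measured plasma glucose concentration > 70 mg/dL (> 3.9 mmol/L) but approaching that level".

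The same SAP section then turns the categories into rules based on three diary items: help needed, any symptoms, and the lowest glucose reading. The rule for the fifth category is "Pseudo: Symptoms (Q2) = Yes and Glucose reading (Q3) = > 3.9 mmol/L". The classification table that follows adds only that assistance is no or missing.

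On what counts, SAP 11.5.3 states: "A subject reported event that does not meet any of the above criteria will not be counted as a hypoglycaemic event". Those unclassified events go to the study team for review.

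On display, SAP 8.2.1.7.3 plans: "Incidence of hypoglycaemia (in total and by each category as defined by ADA criteria) overall and in 3 monthly intervals will be summarised by treatment". For time of day the plan is: "Incidence of daytime hypoglycaemia (in total and by ADA category) and nocturnal hypoglycaemia (in total and by ADA category) will be summarised by treatment". It also plans a table and plots by two-week period (Table 3.25, Figures 3.1 and 3.2), whose titles mention no ADA category.

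**The concern.** The programmed rule is wider than the definition it is meant to carry out. The definition has two conditions on glucose: above 3.9 mmol/L, and near it. The rule keeps the first and loses the second. A symptomatic reading well inside or above the normal range then becomes a type of hypoglycaemic event.

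Two things follow. A total described as hypoglycaemia can contain events that the subject's own meter shows were not low glucose. And the SAP's safety net does not catch them, because it applies only to events that fit no category. With about 17 placebo subjects planned, a handful of such entries could visibly move a rate per arm.

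The list of changes from the protocol in SAP 2.1 does not mention this widening. That same list moves the hypoglycaemia threshold from below 3.9 to 3.9 or below expressly to match the ADA classification.

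**Working it through.** **Step 1: apply the classification table.** The inputs are the rows of the table in SAP 11.5.3. I ran it over assistance (yes/no), symptoms (yes/no) and a range of glucose values in mmol/L.

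| Assistance | Symptoms | Glucose | Result |
|---|---|---|---|
| Yes | any | any, or missing | Severe |
| No | Yes | missing | Probable symptomatic |
| No | Yes | 3.0, 3.9 | Documented symptomatic |
| No | Yes | 4.0, 4.5, 5.5, 7.8, 10.1, 15, 25 | Pseudo, counted |
| No | No | 3.0, 3.9 | Asymptomatic |
| No | No | 4.0 to 25, or missing | Not counted, sent for review |

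Every unassisted symptomatic reading from 4.0 to 25 is treated alike. Under the 7-point profile rules in SAP 11.5.4, a value above 10.0 mmol/L is a hyperglycaemic excursion. The same value in the event diary can be a hypoglycaemia category. The review also works the wrong way round: an asymptomatic 4.0 is flagged, while a symptomatic 15 is not.

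**Step 2: trace where these events go.**
- SAP 11.5.3 drops only events that meet no category, so Pseudo events are counted.
- SAP 8.2.1.7.3 asks for totals and for each category, and excludes nothing from the total. No sentence says that the total includes Pseudo; this follows from reading the two sections together.
- Tables 3.22 and 3.24 are split by ADA category, so a reader can subtract Pseudo event counts. The percentage of subjects cannot be recovered this way, because SAP 11.5.3 places a subject in every category they experience and the percentages do not add.
- Table 3.25 and Figures 3.1 and 3.2 appear unsplit. This is inferred from their titles and the text; no completed shell is given.

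**Step 3: trace where they do not go.**
- The primary endpoint is C-peptide AUC.
- Significant hypoglycaemia (SAP 8.1.1.1 and 11.5.4) is limited to severe, documented symptomatic and asymptomatic events.
- The summary below 3.1 mmol/L cannot contain a reading above 3.9.
- Protocol 8.3.5.4 plans no hypothesis tests on safety variables.

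**Step 4: size.** The documents give no share of Pseudo events, so these are assumptions only. If Pseudo events are a share s of all counted events, the total exceeds a total without them by 1/(1 − s) − 1.
- s = 0.05: 1/0.95 − 1 = 5.3%.
- s = 0.20: 1/0.80 − 1 = 25%.
- With equal rates of the other events, s = 0.15 on albiglutide and s = 0.05 on placebo: (1/0.85)/(1/0.95) = 0.95/0.85 = 1.118, an apparent excess of about 12%.

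These figures treat every Pseudo event as surplus, including readings just above 3.9 that the definition accepts. They are therefore upper limits, for each assumed share, on what the missing ceiling could add. The part well above 3.9 cannot be computed, because neither document puts a number on how close a reading must be.

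**The case against.** A reader might infer that counting Pseudo events in the total is itself contrary to the protocol. It is not. Protocol 6.4.2 makes pseudo-hypoglycaemia one of its five categories, and the safety endpoint in protocol 6.4.1 is incidence in total and by category. Including Pseudo is a natural reading of that endpoint; only the missing ceiling departs from the stated definition. This stands, and it is why the protocol total should be kept.

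A reader might also infer a bias between arms, since protocol 5.1.2 notes that nausea and vomiting may be side effects of albiglutide. The documents do not support that step. The records are events that subjects chose to enter as hypoglycaemic, with the lowest reading at the time, and SAP 11.5.3 says the investigator reviewed them. For nausea and vomiting, protocol 5.1.2 advises more frequent urine checks, not diary entries. An imbalance is possible but not shown.

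The SAP 11.5.3 statement that the summaries take in all reported events might be read as settling that Pseudo is in the total. Its parenthesis shows that it concerns on-therapy and post-therapy phases, so it does not settle the point.

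Finally, with no number for closeness in either document, a plain rule of above 3.9 avoids an arbitrary cut-off, and very high readings in a hypoglycaemia diary may be rare. Both are fair. But the rule does not exclude such readings, and the SAP does not disclose that it has set the qualifier aside.

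**Conclusion.** The point holds in a limited form. The Pseudo rule in SAP 11.5.3 is broader than the definition in protocol 6.4.2 and in the SAP itself. Unassisted symptomatic events with clearly non-low readings, even above 10.0 mmol/L, are counted as hypoglycaemic events without the review given to unclassified events. That they reach the total rows rests on reading SAP 11.5.3 with 8.2.1.7.3; that they reach the 2-weekly displays without a split rests on the titles.

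The effect is confined to descriptive safety summaries, and no efficacy conclusion depends on it. Its size and any difference between arms are unknown; the 5% to 25% and 12% figures are illustrations under assumed shares. It should be corrected before unblinding, because a bound chosen afterwards could be influenced by the results.

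**What to change.** 1. Keep the protocol total of all ADA categories, and add a row for the total excluding Pseudo (severe, documented symptomatic, asymptomatic and probable symptomatic) to Tables 3.22, 3.24 and 3.25. Base Figures 3.1 and 3.2 on that row. State in SAP 8.2.1.7.3 which total is which.
2. In SAP 11.5.3, reconcile the Pseudo rule and its table row with the stated definition. The study team should fix an upper glucose bound before unblinding and record it. Events above the bound are flagged for review and listed, not counted.

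The cost is some SAP wording, one derivation flag and one extra row per table. Counts become slightly lower wherever Pseudo, or its upper part, is left out. No data are lost, because all events remain in the listing.
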